Another potential mechanism favoring efficacy in preventing CHB, is that HCQ by virtue of reducing endosomal acidification might also decrease transplacental transport of maternal antibodies. This possibility is supported by the fact that maternal IgG is pinocytosed at the apical surface of the syncytiotrophoblast into an acid endosomal compartment containing FcRn, and migrates via transport vesicles to the basolateral surface of the cell, where at physiologic pH it uncouples from the receptor (15).

Study Design

Nineteen women in Stage 1 and an additional 51 women in Stage 2 (if reached, for a total of 70 subjects) meeting eligibility criteria will receive 400mg per day of HCQ beginning as soon as pregnancy is established and informed consent obtained. Mothers already on HCQ will remain on 400mg, or escalate to 400mg if on 200mg. The primary investigator, [name]., holds a U.S. Federal Drug Administration-issued IND (Investigational New Drug) number (112357) for HCQ.

A. Screening visit: Prior to the qualifying visit, the consent form will be reviewed and signed. Laboratory tests will include: CBC, liver-function tests (routine chemistries; albumin will be important to standardize the effect of physiologic hemodilution of pregnancy in gauging changes in autoantibody titers), urinalysis, and a 24 h collection for measurement of creatinine clearance and protein excretion as deemed appropriate. Serologic profiles will include: measurement of ANA, anti-DNA, C3 and C4. Blood will be drawn for baseline anti-Ro/La titer HCQ level, and IFNαactivity. Only the former will be available prior to qualification for enrollment. In total, 35 ml of blood will be drawn at screening.

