B. Qualifying Visit: This is done as soon as Ab status is established, which should take several days (ship overnight and assay in [name] laboratory is one day turnaround time; for [name], it is equivalent). A detailed history and physical examination will be performed. The patient will either be given a prescription for HCQ 200mg, 2 tabs hs, and advised to see an ophthalmologist, or told to maintain dose if 400mg. For women who have SLE, data will be collected to calculate the Systemic Lupus Erythematosus Pregnancy Disease Activity Index (SLEPDAI). Rheumatologists will complete assessment forms, which will be reviewed by Drs. [name] and [name] to address any effect of treatment on underlying SLE activity per se. Of note, [name] has provided these forms for use in the ongoing NIH-supported PROMISSE trial.

C. Follow-up Assessments: Fetal echocardiograms will be performed after enrollment (16-18 weeks) and weekly thereafter until 26 weeks, then biweekly until 34 weeks. Fetal echocardiographic scans will be performed according to standard methods [14,33,39], recorded on VHS videotape or DVD/Optical Disc by the pediatric cardiologist or obstetrician, and sent to the core echocardiographic lab and quantified on data abstraction forms by [name]. After the final fetal echo at 34 weeks, patients will continue with routine obstetric and rheumatologic care as appropriate. Neonates will have an EKG and echocardiogram at birth and at 1-year follow-up (it is acknowledged that this will be

out of the window of LFM award but not affect outcome since to date CHB has not occurred de novo after birth). Each woman will undergo routine obstetrical ultrasounds as per the treating obstetrician. Targeted Level 2 ultrasounds will be required between 21-24 weeks, and between 30-32 weeks to assess fetal well-being. Mothers enrolled in Europe will have their echocardiograms initially read by their primary cardiologists with the tapes then forwarded to [name].

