Between 20-25 weeks and 30-35 weeks, and at delivery for all women, 20 ml of blood will be drawn (10 for serum, 10 for plasma and isolation of DNA). Cord blood will also be obtained. Both HCQ levels and IFN-α activity will be evaluated in each sample to serve both as a proxy for compliance and as a potential biomarker of efficacy, respectively. Samples will be sent overnight to [name] lab at each visit (screening, 2nd trimester, 3rd trimester, and delivery), rather than having each site process the bloods, which may be unduly cumbersome for busy obstetrical practices. For patients enrolled in Europe, samples will be stored in [name] lab and shipped in batch. Serum samples will be divided into aliquots of 500 □I: 2 will have sodium azide added (final concentration 0.1%) and be stored at 4oC; remaining samples will be stored without azide at -70oC to form the serum specimen bank available to other investigators with approved research protocols (as in the RRNL). Plasma will be similarly stored. DNA will be stored for future investigations as spawned by the clinical results.

Enrolled patients will continue usual care dictated by their underlying rheumatic disease.

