HCQ levels, This assay will be done in [name] laboratory in France. At each patient encounter, the interval between the last ingestion of HCQ and blood sampling is recorded. HCQ is assayed by HPLC with fluorometric detection as described [35] with minor modifications. The detection limit is 10ng/ml, and the between-day and within-day coefficients of variation are <8%.

IFNα activity: This assay will be done in [name] laboratory and will utilize the WISH cell assay, as we have previously reported in anti-Ro positive mothers of children with neonatal lupus [40].

The reporter WISH cells are incubated with 50% patient plasma or serum for 6 hours. Total mRNA is purified from WISH cell lysates and cDNA synthesized from total mRNAs. Forward and reverse primers are used for the genes MX1, PKR, and IFIT1, which are highly and specifically induced by type I IFN. The relative expression of each of the 3 tested IFN-induced genes is calculated as a fold increase compared to its expression in WISH cells cultured with media alone. The ability of patient serum to cause IFN-induced gene expression in the reporter cells is then compared to the mean and SD induced by healthy donor serum. The number of SD above the mean of healthy donors for each gene is calculated. Data are expressed quantitatively as the sum of the number of SD of each of the three genes above the mean of healthy donors. The 3 transcripts chosen for measurement represent coordinate activation of the IFN- α pathway as would be expected after ligation of the type I IFN receptor, instead of measurement of only one IFN- α -induced transcript which may not accurately represent pathway activation. Patients are considered to have high type I IFN activity if either of the two following criteria are met: 1) 2/3 tested IFN-induced genes are expressed >1 SD above the mean of healthy donors, and at least 1 is greater than or equal to 2 SD above the mean of healthy donors, or 2) 1 IFN-induced gene is expressed greater than 4 SD above the mean of healthy donor sera. If neither criterion is met, the sample is considered to have low type I IFN activity. Two-sided Fisher's exact test (sum of small p's method for observed \geq expected) is used to analyze the categorical data, and Mann-Whitney non-parametric t-test is used to compare quantitative data. All evaluations will be done in batch (with the exception of screening anti-Ro/La) when the patient has completed the study.

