verify Ab in his laboratory. 2) Mothers must have a previous child with cardiac NL, defined herein as: the presence of heart block (1st, 2nd, or 3rd degree) documented by electrocardiogram (EKG), echocardiogram, pacemaker, or statement in the medical record, and/or; presence of cardiac injury, which specifically includes autopsy evidence of a mononuclear infiltrate in the endocardium, myocardium, and pericardium and/or EFE on echocardiogram always associated with cardiac dysfunction. In PITCH, we included women with a prior child with rash; however, recent data generated from the RRNL suggest that recurrence of CHB following rash is 11%, not 18% [34]. Thus, inclusion of previous rash could lead to a falsely lowered recurrence rate, and will therefore be excluded. 3) Intrauterine pregnancy \leq 12 weeks. 4) Mother may be taking \leq 20 mg prednisone because, in our experience, CHB has developed in the presence of this dose. 5) Mother may be asymptomatic, or have a rheumatic disease such as SLE or SS. Maternal health status has not been considered an influence on the development of CHB [1]. 6) Mother may or may not already be taking HCQ. This latter point was discussed with [name], who has published extensively on measurement of HCQ [35,36]. While it might be optimal for the mothers anticipating enrollment in the study to all have been on HCQ prior to conception, this is impractical. Some may never achieve pregnancy and not want to take HCQ unless they conceive (especially those asymptomatic). On the other hand, women with SLE are likely to already be on HCQ and it would limit enrollment to exclude these patients if all must initiate HCQ only at enrollment in the first trimester. Although the accepted dogma is that HCQ requires several months for maximal efficacy in treating rheumatic disease, it is unknown whether this would apply to transplacental passage or fetal levels (which are impossible to measure). [name] suggests that HCQ is probably a three compartment model which includes the circulation, tissues and cells. In the circulation, the half life is approximately 7 days and in the tissues, it is 40 days [37,38]. In [name] experience, steady state blood levels of HCQ are achieved in 4-6 weeks. Thus, dosing the mother no later than 10 weeks gestation should provide sufficient fetal exposure before the vulnerable period of CHB which is generally accepted to span 18-24 wks. Furthermore, the placenta has to be formed for HCQ to gain access to the fetus and it may be effective quickly for the biology we are considering.

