The proposed design has the following operating characteristics. Let p1 = recurrence rate definitely not worthy of further investigation; p2 = recurrence definitely worthy of further investigation. In this study, we define p1 = 18% [41] and p2 = 5%. According to Simon's optimal 2stage approach [32], the expected sample size is 29.8 subjects with a probability of early termination of 0.69 when the recurrence rate is equal to p1. The probability of accepting the treatment for further study is at most 5% if the recurrence rate is unacceptably high (>18%) with that treatment. In contrast, there is a 90% probability of accepting the treatment for further study if the true recurrence rate is 5%. It is important to emphasize that the purpose is to obtain critical data on the efficacy of HCQ in the prevention of recurrent CHB and determine whether this preventive approach should be studied further. At study completion, the proportion of mothers having a child with advanced CHB will also be computed, along with corresponding 95% confidence intervals. Secondary endpoints that are binary (i.e., occurrence of 1st degree block, abnormal fluid collection) will be analyzed by similar approaches. Continuous variables (e.g., shortening fraction, gestational age) will be summarized by estimating means and standard deviations. The effect of therapy on HCQ levels, IFN-α signatures, and Ab titers will be evaluated by fitting mixed effects linear models to repeated assessments of titers obtained during follow-up. In addition, change in any of these analytes at specific time points from baseline will be analyzed using the paired t-test or Wilcoxon signed rank test, depending on distribution of the data.

Safety committee. An independent DSMB will convene by teleconference three times during the year. The members include Drs. [name], [name], and [name] (all of whom served in PITCH).

Data Storage and Confidentiality

Data management. Study information will be recorded at the patients' obstetrical and rheumatology sites. Standardized, computer-adapted case report forms (CRFs) have been developed. Within 2 weeks of each visit, completed CRFs and tapes of the echocardiograms will be sent to [name]. Following review, CRFs will be faxed to the coordinator at NYU for final error checks and entered into the computer database. The coordinator will maintain a calendar for each patient, monitor completion

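### The paired change-from-baseline tests for HCQ level, IFN-alpha activity and antibody titre do not separate women by HCQ use at screening, so they mix new starters, women stepped up from 200 mg and women with no dose change.

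*Combined protocol and SAP*

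**What the plan says.** All places are in the combined protocol and SAP.

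- **Statistical considerations for overall study.** The effect of therapy on HCQ levels, IFN-alpha signatures and antibody titres "will be evaluated by fitting mixed effects linear models to repeated assessments of titers obtained during follow-up". The next sentence adds that "change in any of these analytes at specific time points from baseline will be analyzed using the paired t-test or Wilcoxon signed rank test", the choice depending on the distribution. Neither sentence names a stratum, subgroup or covariate.
- **Screening visit.** "Blood will be drawn for baseline anti-Ro/La titer HCQ level" and IFN-alpha activity. This draw precedes the prescription given at the qualifying visit.
- **Eligibility (Inclusion) Criteria, item 6.** "Mother may or may not already be taking HCQ". The same item expects many women with SLE to be on the drug already, and puts steady-state blood levels at 4-6 weeks.
- **Study Design.** "Mothers already on HCQ will remain on 400mg, or escalate to 400mg if on 200mg". The Qualifying Visit section confirms the no-change group: women are given a prescription "or told to maintain dose if 400mg".
- **Follow-up Assessments.** HCQ level serves as a proxy for compliance, and IFN-alpha activity "as a potential biomarker of efficacy".
- **IFN-alpha activity.** Fisher's exact test is named for categorical data, and "Mann-Whitney non-parametric t-test is used to compare quantitative data". The groups to be compared are not defined.

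**The concern.** A paired test on change from baseline has a clear meaning when baseline is the same state for everyone. Here it is not. For a woman who starts HCQ in the trial, the change runs from off-drug to on-drug. For a woman on 200 mg it is a dose step. For a woman kept on 400 mg it compares two on-drug samples, and if she has taken the drug longer than the 4-6 weeks quoted for steady state, her level may already have settled at screening.

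The problem is plainest for HCQ level itself: new starters begin near zero and established users do not, so a pooled mean change describes neither. For IFN-alpha activity, if already-treated women change less than new starters, the pooled change understates what happens when HCQ is started and could be misread as a lack of biological effect.

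The stake is limited. These biomarkers are not among the eight listed secondary outcomes and play no part in the rule that decides whether HCQ is effective.

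**Working it through.** The plan gives no sample size, effect size or power for these tests, so there is no stated figure to reproduce. The check has a reading part and an illustration.

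**Entry groups and what the paired change measures**

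| HCQ at screening | Assigned dose in trial | Contrast in the paired change |
|---|---|---|
| None | 400 mg | off-drug to 400 mg |
| 200 mg | 400 mg | 200 mg to 400 mg |
| 400 mg | 400 mg | no dose change |

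No section separates these rows in the analysis. The mixed model is described as fitted to assessments made during follow-up, when every woman is assigned 400 mg. It has the same problem only if the screening sample is included.

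**Size of the dilution (illustration)**

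Let n0, n200 and n400 be the numbers not on HCQ, on 200 mg and on 400 mg at screening. Let c200 and c400 be each treated group's mean change as a fraction of the new-starter change. Then

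pooled change / new-starter change = (n0 + n200 × c200 + n400 × c400) / N.

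Only N = 19 (Stage 1) and N = 70 (both stages) come from the documents. All group sizes and c values are assumed.

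Example, 10/2/7 with c200 = 0.5 and c400 = 0: (10 + 2 × 0.5 + 7 × 0) / 19 = 11/19 = 0.579.

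| n0/n200/n400 | c200 = 0.5, c400 = 0 | c200 = 0.75, c400 = 0.5 | both 1 |
|---|---|---|---|
| 10/2/7 | 0.579 | 0.789 | 1.000 |
| 13/1/5 | 0.711 | 0.855 | 1.000 |
| 6/3/10 | 0.395 | 0.697 | 1.000 |
| 35/7/28 | 0.550 | 0.775 | 1.000 |

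If already-treated women change more than new starters, the ratio passes 1: 10/2/7 with both c = 1.2 gives (10 + 2.4 + 8.4) / 19 = 1.095.

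**Precision cost of separating the groups**

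95% CI half-width in units of the SD of change = t(0.975, n − 1) / √n. For n = 19: 2.101 / 4.359 = 0.482.

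| n | 6 | 10 | 13 | 19 | 35 | 70 |
|---|---|---|---|---|---|---|
| half-width | 1.049 | 0.715 | 0.604 | 0.482 | 0.344 | 0.238 |

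**Power, pooled against new starters alone**

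Assumptions: two-sided 0.05 paired t-test, noncentral t; new-starter change d in within-group SD units (d = 0.8 for N = 19, d = 0.4 for N = 70); pooled SD including the spread between groups.

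| Split | New starters alone | Pooled, c200 = 0.5, c400 = 0 | Pooled, c200 = 0.75, c400 = 0.5 |
|---|---|---|---|
| 10/2/7 | 0.62 | 0.43 | 0.73 |
| 13/1/5 | 0.75 | 0.60 | 0.79 |
| 6/3/10 | 0.36 | 0.23 | 0.62 |
| 35/7/28 | 0.63 | 0.43 | 0.72 |

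The ranking follows the assumption. Separation wins if women on 400 mg do not change; pooling wins if they change half as much as new starters.

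**The case against.** The best defence is that the plan never says the paired change estimates the effect of starting HCQ. The trial enrols users and non-users on purpose and explains why, and the average change in that cohort is a legitimate description. The text is silent on subgroups; it does not order pooling. The split can still be made at analysis because the data are collected. For maternal antibody titre there is little reason to expect a difference by entry status, since the mechanism proposed is reduced placental transport. The illustrative ratios run from 0.39 to 1.10 and include 1.00. Separation would not isolate a drug effect either, as gestation changes over the same visits.

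Much of this stands. The size and even the direction are unknown, the case is weaker for titre than for HCQ level, power gives no general argument for separation, and no trial decision depends on the result. Two parts do not stand. The paired-test sentence is introduced as an addition directly after the one on the effect of therapy, so a reader will take the change as evidence on that effect, and a woman whose baseline is already on 400 mg cannot supply it. A split chosen after the data are seen also carries less weight than one fixed beforehand, especially with 19 to 70 women.

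**Conclusion.** The concern holds, as a low-priority improvement. As written, the paired tests average three different exposure contrasts, including women with an on-drug baseline and no dose change. That follows from the text without any assumption. How far the pooled change departs from the new-starter change cannot be derived from the documents; it depends wholly on the mix at entry and on how much already-treated women change. The argument for separation is that the reader then knows which contrast is being estimated, not that power improves. The point is confined to the paired tests, and to the mixed model only if the screening sample enters it. The between-group IFN tests are a separate analysis with undefined groups, so paired change is not the only IFN result. The primary outcome and the two-stage rule are untouched.

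**What to change.** Amend Statistical considerations for overall study as follows:

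1. Report paired changes from baseline by HCQ status at screening, with the number of women in each group: at least not on HCQ versus already on HCQ, with 200 mg shown separately if numbers allow.
2. Define status from the medications case report form and the baseline HCQ level, and say beforehand which governs if they disagree.
3. Take the change on starting HCQ from women not on it at screening. Label any pooled change as a mixture.
4. If the mixed model includes the screening sample, add entry status and its interaction with visit where numbers allow. With 19 women, two levels of status may be the most the data support.
5. Call any comparison between status groups exploratory, because the eligibility text ties prior use to SLE.

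The cost is wording only; both data sources are already collected. The downside is precision: with the assumed splits, the half-width goes from 0.48 SD (19 women) to 0.72 SD (10 new starters), or from 0.24 SD (70) to 0.34 SD (35). Without a control arm, the change in new starters will still include gestational effects, and the report should say so.

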Hydroxychloroquine is part of a group of medications initially used to treat malaria, but usage has expanded to rheumatologic conditions such as systemic lupus and rheumatoid arthritis. Even though the U.S. Food and Drug Administration (FDA) lists hydroxychloroquine as a medication that has not been determined to be safe in pregnancy, extensive review of the medical literature suggests that this drug is safe during pregnancy. Results from animal studies showed that hydroxychloroquine could have visual side effects on the baby and there are also isolated case reports of hearing and visual problems in babies whose mothers received this drug during pregnancy. However, none of the clinical studies (inclusive of over 300 children) using hydroxychloroquine during pregnancy have found a higher frequency of hearing problems, visual problems or any other malformation in the babies exposed to the medication during pregnancy than in pregnancies in which the baby's mother did not take hydroxychloroquine. The potential side effects for the mothers are rare and consist of temporary gastrointestinal discomfort, discoloration of the skin and visual problems. A patient taking this drug should be seen by an eye doctor once per year and therefore if you have never been on this drug and are taking it only for this study, you should see an eye doctor. Two pills each day is the dose of hydroxychloroquine used for this study and both pills can be taken together.

With regard to having blood drawn, minor bruising at the site of blood drawing is common. Less common are larger bruises, inflammation of the vein where the blood was drawn, infection, and blood clots. Rarely, people faint from having blood drawn. We will draw your blood while you are sitting or lying on your back and ask you to remain in that position for several minutes to further minimize the risk of fainting. The risk of removing the amount of blood required for the study is minor. The additional amount of blood drawn only for this study is not large (1 tablespoon at each visit) and does not pose an additional risk to you or your unborn child.

No independently confirmed adverse effects on the fetus resulting from prenatal diagnostic ultrasound exposure have been reported. Acoustic output (the amount of sound applied to the mother's abdomen to produce the ultrasound image of the fetal heart) will be kept below acceptable limits.

Protection Against Risks

Safety committee. An independent DSMB will convene by teleconference three times during the year. The members include Drs. [name], [name], and [name] (all of whom served in PITCH).

Individual stopping rules: Fetal: 1) Development of advanced block (2nd or 3rd degree); 1st degree block will not constitute a formal stopping point. 2) Decrease of amniotic fluid index <5 cm. 3) Intrauterine growth restriction (IUGR) - no fetal growth over 2 weeks. 4) Hydrops or myocardial dysfunction or EFE. 5) Death. Maternal: 1) Serious reaction to study drug, e.g. severe rash or intractable G.I. intolerance. 2) Withdrawal of consent. If isolated 1st degree heart block occurs, dexamethasone may be offered, and the patient may continue in the study. If a patient achieves an individual stopping point due to CHB and hydropic changes, she will be offered dexamethasone and the outcome of the pregnancy will be prospectively followed.

Study stopping rules: Enrollment is stopped if 3 fetuses develop 2nd or 3rd degree block.

Potential Benefits to the Subjects

We hope that this study shows that treatment with hydroxychloroquine prevents the development of heart block in your baby.

The potential benefits are substantial in relation to the small risks posed by participation.

This study is important because there is information from basic science research suggesting that hydroxychloroquine may be effective in preventing the inflammation and fibrosis which may result in heart block. This is only testing done with test tubes, not animals or humans. There is also a large study that reviewed the charts of many women with anti-Ro antibodies and this study found that hydroxychloroquine may be beneficial. However, we also are not sure whether for those mothers who received hydroxychloroquine, they may have had normal babies even without taking the drug. The results of this study will be used not only for a potential benefit to your own baby but also as a guide to help other pregnancies in which the baby is at risk for heart disease.

Subject Identification, Recruitment and Consent/Assent

Method of Subject Identification and Recruitment

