Specific Aim: To determine whether hydroxychloroquine use during pregnancy prevents the recurrence of CHB.

This will be approached in an open label Phase II trial entitled: Preventative Approach to Therapy for Congenital Heart Block with Hydroxychloroquine (PATCH), in pregnant women who have had a previous child with CHB. This is designed as an open-label trial employing Simon's 2-stage optimal

design to allow for early stopping due to absence of treatment efficacy. The first stage requires 19 subjects, which are expected to be enrolled in the year of this award. Despite the rarity of disease and the requirement of a previous child with CHB, based on the US Research Registry for Neonatal Lupus (RRNL) and data from the UK, this proposal is feasible. If 3 mothers have a child with 2nd or 3rd degree CHB, the study is terminated after the first stage. Serial echocardiograms (monitor PR interval) and evaluation of biomarkers (HCQ levels, IFN*a* signatures, and Ab titers) will be part of the protocol. The results of this study should become an integral component of the counseling of women with anti-Ro/La Ab who are considering pregnancy.

Background

CHB associated with maternal anti-Ro Ab has a high mortality (20-30%, primarily fetal/neonatal) and morbidity (67% require permanent pacing before adulthood) [6,7]. In addition to conduction disease, 10-15% of affected offspring will have a life-threatening cardiomyopathy [8,9]. Histopathologic studies constitute a major basis for formulating hypotheses regarding the pathogenesis of CHB, which in turn guide the rationale for therapeutic approaches. Studies of several fetal hearts identified in utero with CHB or isolated myocarditis revealed that fibrosis is extensive and replaces the AV node, even in 20 and 22 week hearts [10], supporting the clinical observation that 3rd degree CHB is irreversible. The identification of a macrophage infiltration in fetuses dying most proximate to the time of diagnosis suggests that inflammation may be integral to the development of fibrosis [10].

Prenatal Considerations

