Characteristics of the Research Population

Number of Subjects and Subject Recruitment

Stage 1, 19 subjects will be given HCQ. If fewer than 3 recurrences are observed, an additional 51 subjects will be treated in Stage 2 (Years 2-3, seeking a renewal and/or NIH funding). However, if 3 or more recurrences are observed after Stage 1, it will be concluded that HCQ is not effective in preventing CHB. Ultimately, HCQ will be considered efficacious for CHB if fewer than 6 CHB cases occur among 70 subjects evaluated on no potentially confounding medications.

While some subjects will be prescribed the study drug (HCQ) by the PI, [name], or a designated study team member (covered by Consent Form Version 1), many patients will be referred to the study from other sites. In these cases, patients' own doctors will take responsibility for prescribing the study drug, and patients will consent to have their bloods and medical records sent to the investigators at NYU for data and sample analysis (as delineated in Consent Form Version 2). [name] or another study team member will discuss the study with each potential subject and complete the informed consent process prior to enrollment. All subjects (74 in total) will be considered enrolled at NYU and consented using NYU IRB-approved consent forms.

Gender of Subjects

Because the aim of this study is to determine whether hydroxychloroquine use during pregnancy prevents congenital heart block, only female subjects will be recruited.

Age of Subjects

18-45

Racial and Ethnic Origin

No subject will be excluded from participation in this study on the basis of race or ethnic origin.

Eligibility (Inclusion) Criteria

1) Mothers must have anti-Ro and/or anti-La Ab documented in the NYU immunology laboratory (CLIA-approved), which utilizes an ELISA (Immunovision) as well as reactivity on ELISA to at least one of three recombinant antigens (48La, 52Ro, 60Ro, JB laboratory). [name] will likewise

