With over 400 families now enrolled in the RRNL and our success at rapid enrollment in PITCH, we are well positioned to enroll in the current study. Most of the women enrolled in the RRNL are of childbearing age, motivation is quite high, and based on review of overall data, it is likely that at least 20% will again become pregnant and available for this study. Importantly, PRIDE and PITCH solidified a referral base of obstetricians and pediatric cardiologists. Furthermore, [name] has agreed to participate given that all 19 patients must be recruited in one year. The DSMB for the U.S. based PITCH study ([name], maternal-fetal medicine, [name], rheumatologist with expertise in pregnancy and women's health issues, and [name], rheumatologist with expertise in design and monitoring of clinical trials in SLE) in conjunction with Drs. [name], [name], [name] (pediatric cardiologist), and [name] (statistician) have had extensive discussions regarding the results of PITCH and the design of this current study. With regard to a randomized trial comparing any drug with placebo, [name] prepared the following analysis:

Assumptions 1. Recurrence rate of CHB (whether previous child had CHB or rash) is approx 19%.

2. Clinically meaningful outcome would be at least 50% reduction in recurrence rate.

Power Calculations 19% to 10% recurrence rate: 261 per group (N = 522)

19% to 5% recurrence rate: 97 per group (N = 194)

Data Analysis And Data Monitoring

Statistical considerations for overall study:

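### The study-level stop at 3 affected fetuses names no stage or denominator; read literally in Stage 2, it conflicts with the success rule of fewer than 6 cases among 70

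*Combined protocol and SAP*

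**What the plan says.** Three places in the combined protocol and SAP use a count of 3.

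- Specific Aim: "If 3 mothers have a child with 2nd or 3rd degree CHB, the study is terminated after the first stage".
- Number of Subjects and Subject Recruitment: "if 3 or more recurrences are observed after Stage 1, it will be concluded that HCQ is not effective in preventing CHB".
- Protection Against Risks, in the only line headed as a study-level stopping rule: "Study stopping rules: Enrollment is stopped if 3 fetuses develop 2nd or 3rd degree block".

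The first two tie the count to Stage 1, which has 19 women. The third names neither a stage nor a denominator, and it does not say what is concluded once enrolment stops.

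Number of Subjects and Subject Recruitment also describes what follows a Stage 1 with fewer than 3 recurrences: "an additional 51 subjects will be treated in Stage 2 (Years 2-3, seeking a renewal and/or NIH funding". The final rule there is that "HCQ will be considered efficacious for CHB if fewer than 6 CHB cases occur among 70 subjects". Totals of 3, 4 and 5 among 70 therefore count as efficacy, provided that no more than 2 fell in Stage 1.

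**The concern.** Within Stage 1 the three statements agree. In Stage 2 they agree only if the line under Protection Against Risks is understood to have lapsed, and nothing in that line says so. Suppose Stage 1 ends with 2 cases among 19 and one more occurs in Stage 2. The recruitment section allows the trial to run on to 70 women and still succeed. The stopping line, as written, closes enrolment.

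The question would then have to be settled after a third case is known, in an open-label, single-arm study. One choice halts a course that may meet the efficacy rule. The other departs from the written stopping rule. A trial closed short of 70 would also have no defined conclusion, because the final rule is stated only for 70 women.

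**Working it through.** **Inputs.** Stage sizes of 19 and 51, total 70 (Study Design). Continue with at most 2 cases among 19; success with at most 5 among 70 (Number of Subjects and Subject Recruitment). Recurrence rates of 18% (unacceptable) and 5% (acceptable) (Data Analysis And Data Monitoring). All calculations are exact binomial and treat every woman as evaluable.

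**The plan's own figures first.** Data Analysis And Data Monitoring states early termination of 0.69 and an expected sample size of 29.8 at 18%, and 90% power at 5%.

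- Early termination at 18%: P(Bin(19, 0.18) ≥ 3) = 0.691. This reproduces.
- Expected size with 70 women: 19 + (1 − 0.691) × 51 = 34.8. The stated 29.8 does not reproduce.
- Power at 5% with 70 women: 0.8315 (derived below). The stated 90% does not reproduce.

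The stated values fit a total of 54 with the same cut-offs (expected size 29.81, power 0.903). That mismatch is a separate issue; 83% is used here because it follows from the 70-woman rule.

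**Acceptance under the two-stage rules at 5%.** Sum over x Stage 1 cases of P(Bin(19) = x) × P(Bin(51) ≤ 5 − x):

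| x in Stage 1 | P(x of 19) | P(at most 5 − x of 51) | Product |
|---|---|---|---|
| 0 | 0.3774 | 0.9589 | 0.3619 |
| 1 | 0.3774 | 0.8896 | 0.3357 |
| 2 | 0.1787 | 0.7494 | 0.1340 |

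The total is 0.8315 (the rounded products sum to 0.8316). Stage 2 opens with probability P(Bin(19) ≤ 2) = 0.933.

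**How often the two rules meet.** The probability of at most 2 cases among all 70 is P(Bin(70, 0.05) ≤ 2) = 0.3137. All such trials are also successes under the two-stage rules. The remaining successes have a third case in Stage 2 and finish with 3, 4 or 5 cases: 0.8315 − 0.3137 = 0.518 of all trials, or 0.518 / 0.8315 = 62% of successes. Given that Stage 2 opens, the chance of a third case by woman 70 is 1 − 0.3137 / 0.9335 = 0.664.

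**Allowing for detection lag.** Block is seen weeks after enrolment, so more women will have joined by then. The documents do not give this number, so it is an assumption:

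- Even accrual of 51 women over Years 2-3 (104 weeks): 51 / 104 = 0.49 per week.
- Enrolment at 5 to 12 weeks of gestation. The upper limit is from the inclusion criteria; the lower is assumed.
- Detection at 18 to 25 weeks. Eligibility gives a vulnerable period of 18-24 weeks, and the earlier US IVIG study saw cases at 19, 20 and 25 weeks.
- Lag: from 18 − 12 = 6 weeks to 25 − 5 = 20 weeks, or 0.49 × 6 = 2.9 to 0.49 × 20 = 9.8 women.

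If L further women are already enrolled when the third case is known, the literal stop cuts enrolment short whenever that case falls among the first 69 − L women.

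| L | All 70 enrolled: P(Bin(69 − L) ≤ 2) | Cut short on a two-stage success |
|---|---|---|
| 3 | 0.353 | 0.479 |
| 10 | 0.429 | 0.403 |

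The last column is 0.8315 minus the probability that at most 2 of the first 69 − L women and at most 5 of all 70 are cases.

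**The case against.** The best defence is that the protocol, read as a whole, has one 3-case boundary and one 6-case boundary. The Specific Aim and the recruitment section use the same count and the same event, and both place it in Stage 1. The surrounding text is written for a one-year Stage 1 award: Methods and Procedures says that "all 19 patients must be recruited in one year", and the monitoring text beside the stopping line says "An independent DSMB will convene by teleconference three times during the year". Stage 2 is contingent on further funding. On that reading the stopping line restates the Stage 1 rule and the conflict disappears.

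Most of this stands, and shorthand is the likelier explanation. What remains is that the line itself is unscoped. It sits in a study-wide protection section beside individual stopping rules that carry no stage limit. It acts on enrolment as cases develop, whereas the recruitment section's boundary is read after Stage 1. The Background also describes the 3-case stopping rule of the earlier US IVIG study without naming a stage. The literal reading is therefore open to someone applying the protocol in good faith.

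Two stronger readings are not supported:

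- A reader might infer that the chance of success falls from 83% to 31%. The 31% is the probability of at most 2 cases in 70 with no detection lag. It becomes a success rate only if a stopped trial is counted as a failure, which the documents nowhere say, and zero lag is unrealistic on this echocardiogram schedule.
- A reader might infer that the monitoring board holds two conflicting instructions. The documents give the board no stated role in applying either numerical boundary.

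**Conclusion.** The point holds as an internal inconsistency that should be fixed. It does not show that the protocol contains a second, competing stopping rule. The stopping line lacks a stage and a denominator, and its literal application in Stage 2 conflicts with the efficacy rule.

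At 5% recurrence the overlap is large: 52% of all trials reach a third case by woman 70 on a course that counts as success, and about 40% to 48% would have enrolment cut short on such a course. The first figure rests on the 5% rate and all women being evaluable. The range rests also on the assumed 3 to 10 women enrolled during the detection lag. Neither has any consequence unless Stage 2 opens and the line is applied study-wide.

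**What to change.** Before Stage 2 opens, reconcile the Specific Aim, Number of Subjects and Subject Recruitment, and the study stopping rule under Protection Against Risks, so that the 3-case rule states its stage and denominator everywhere.

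- If the two-stage design is what is intended, say under Protection Against Risks that the rule is the Stage 1 boundary, counted among the first 19 women. This costs one or two sentences and needs no extra data or patients.
- If a study-wide stop at 3 cases is intended, say so, state what is concluded when enrolment stops, and restate the success rule and operating characteristics to match. This requires a recalculation of the design.

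Which of the two is meant is for the sponsor and investigators to decide.
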